The content of the cluster headache diary is developed on key characteristics as mentioned in the definition of cCH (see section 9.1.2). The eDiary consists of applications and reports which will be used to derive the cluster headache endpoints and abortive medication use. The patient should record for each day/week if they experienced any cluster headache attacks. For each experienced cluster headache attack, the start date and time will be collected. The patient will record further daily/weekly information regarding the severity of pain associated to cluster headache and intake of cluster headache abortive medication. Cluster headache items will be assessed with a yes/no response; and severity of pain will be rated on an ordinal scale ranging from 0 to 4 (headache pain ratings: 0=none/barely any pain; 1=mild; 2=moderate; 3=severe; 4=excruciating).⁴⁸ Additional details regarding the questions that patients will answer can be found in the *eDiary Training Module*.

The Screening Visit will correspond to the day of eDiary distribution and will start the 28-day eDiary Screening Period. Any patient found to be ineligible for the study during Screening Period will not be enrolled. An *eDiary Eligibility Report* will be used to review baseline cluster headache attack days and eDiary compliance during the Screening Period for the eligibility assessment of:

- a minimum 14 cluster headache attacks for the first 28 days of Screening Period
- compliance by entry of cluster headache data for at least 24 out of the first 28 days of Screening Period.

On the Baseline Visit (Day 0/Visit 2), patients must ensure to complete eDiary recording of cluster headache attacks that ended prior to infusion (that is for cluster headache attacks which are ongoing or not yet recorded in the eDiary).

On each day during the first 4 weeks that follow each eptinezumab infusion, the patient will be asked to record eDiary data for the day. On Weeks 5 to 12, 17 to 24, 29 to 36, and 41 to 48, and until the Completion Visit (Week 48/Visit 14)/Withdrawal Visit, the patient will be asked to record eDiary data for the week.

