The following visits will be site visits: Screening Visit at Week -4 (Visit 1), Investigational Medicinal Product (IMP) Visits at Weeks 0, 12, 24 and 36 (Visits 2, 5, 8 and 11), Completion Visit at Week 48 (Visit 14) and SFU Visit at Week 56 (Visit 15) or Withdrawal Visit, if applicable. All other trial visits will be phone contact visits. In exceptional situations to be approved by the Contract Research Organisation's (CRO) medical monitor, site visits may only consist of blood and urine sampling (for clinical safety laboratory tests, exploratory eptinezumab quantification, ADA including NAb, and exploratory biomarkers), ECG, vital signs, physical and neurological examinations, adverse events recording, and eptinezumab administration, while the remaining assessments (eDiary, electronic participant-reported outcomes [ePROs], C-SSRS, and investigator evaluations) can be conducted remotely as virtual clinic visits in line with the United States Food and Drug Administration (US FDA) and European Medicines Agency (EMA) guidance.

Participants will be assigned an eDiary at the beginning of the Screening Period (Visit 1, Week -4) and will be required to complete it:

- Daily - during the Screening Period (from Week -4 to Day 0) and during the first 4 weeks that follow each eptinezumab infusion (Weeks 1 to 4, 13 to 16, 25 to 28, and 37 to 40).
- Weekly - for Weeks 5 to 12, 17 to 24, 29 to 36, and 41 to 48.

[figure not shown]
During the trial visits with eptinezumab infusion, eDiary and ePROs must be completed prior to infusion and prior to any interaction with the clinical site staff.

At these visits, safety assessments will be performed before and after the infusion. Safety assessments before eptinezumab infusion consists of vital signs including body temperature, weight, concomitant medications, adverse events, ECG, blood sampling (for clinical safety laboratory tests, exploratory eptinezumab quantification, and ADA including NAb), urine sampling (for clinical safety laboratory and pregnancy tests) and C-SSRS. Safety assessments after eptinezumab infusion consists of vital signs including body temperature, and adverse events.

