23.2.1.3 Imputation of Missing Post-baseline eDiary Assessments

The strategy of imputation of missing values is given by:

1. For each weekly score in the periods with daily entries in the eDiary, prorating is used to impute any missing data when data have been observed for at least 4 days in a week, to have full weekly scores
2. For each monthly score, prorating is used to impute any missing data when data have been observed for at least 2 weeks in a month (after prorating weekly scores), to have full monthly scores

For a 7-day weekly period where the eDiary is completed in at least 4 out of 7 days, the number of attacks will be calculated using prorating:

$7 * (\text{Reported number of daily attacks/Reported eDiary Days})$

For participants where the eDiary is completed in 3 days or less, the 7-day weekly observation will be set to missing.

For a 4-week monthly period where the eDiary is completed in at least 2 out of 4 weeks, the number of attacks will be calculated using prorating:

$4 * (\text{Number of weekly attacks/Reported eDiary Weeks})$

For participants where the eDiary is completed in 1 week or less the 4-week monthly observation will be set to missing.

Use of abortive medication is prorated using the same criteria and formulas as above where *Reported number of daily attacks* is replaced by *Reported number of daily times an abortive medication was taken* and *Number of weekly attacks* is replaced by *Number of weekly times an abortive medication was taken*.

The severity of attacks is prorated using the same criteria as above using the same formulas as in section [23.2.1.2](#).

The derivation of the three pain scores can be seen in [Panel 5](#). When calculating the average attack related daily pain and the weekly integrated measure of frequency and intensity of attack related pain, a value of 0 will be added to the nominator and count as a day in the denominator for days/weeks with 0 attacks. Furthermore, the weekly pain per attack is not defined for days/weeks with 0 attacks.

Panel 5 Definitions of Post-Baseline Pain Scores

	Daily eDiary	Weekly eDiary
Average attack related daily pain	Sum of the average daily pain across days with data/number of days with data	NA
Weekly pain per attack	Sum of pain across attacks/number of attacks	Pain
Monthly pain per attack	Sum of the weekly pain per attack scores/ number of the weekly pain per attack scores	

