23.2.1.5 Calculation of Assessments for Intercurrent Events

Withdrawal from Treatment

When considering withdrawal from treatment data that are collected 3 months or more after the latest infusion will be excluded. Thus, for the daily entries, data occurring 84 days or more after the date for withdrawal from treatment will be removed. For the weekly entries, if at least one day of the 7-day period is covered by 84 days or more then data will be removed.

Use of Transitional Treatment

When considering the use of transitional treatment, data are excluded 7 days after the use of transitional treatment. Thus, for the daily entries, data that occur on 1 to 7 days after the date of use of transitional treatment will be removed. For the weekly entries, if the 7-day period is including at least 1 of the days in the 7-day period after use of transitional treatment data will be removed.

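### In weekly-diary weeks the transitional-treatment rule deletes valid pre-treatment days; if treatment follows a worsening, the monthly count falls below the estimand's own target

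*SAP*

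**What the plan says.** SAP 23.2.1.5 gives two rules for one intercurrent event. For daily entries, "data that occur on 1 to 7 days after the date of use of transitional treatment will be removed". For weekly entries, the whole entry goes if its 7-day period "is including at least 1 of the days in the 7-day period after use of transitional treatment data will be removed". Nothing retains the part of a weekly entry that precedes treatment.

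The diary schedule (SAP chapter 2) is "Weekly - for Weeks 5 to 12, 17 to 24, 29 to 36, and 41 to 48", with daily entries in the four weeks after each infusion.

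SAP 23.2.1.3 then fills the gaps. Within a daily-diary week, "prorating is used to impute any missing data when data have been observed for at least 4 days in a week"; with 3 days or fewer the week is missing. Within a month, "prorating is used to impute any missing data when data have been observed for at least 2 weeks in a month", and the score is 4 times ("Number of weekly attacks/Reported eDiary Weeks").

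The data set built this way, DPS3, feeds the long-term estimand (SAP chapter 6 and 13.5.3) and all response analyses, including their LOCF and worst-case versions (13.5.6.2). The strategy is hypothetical, and 13.5.1.1 calls it conservative because transitional treatment is expected to help. SAP 13.5.9.1 adds an all-data analysis (DPS1) for the short-term and long-term estimand endpoints only.

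**The concern.** Attacks before transitional treatment are valid data for a target in which that treatment does not exist; only the period after it is contaminated. The weekly rule discards both. Transitional treatment is likely to be given when attacks have become more frequent. In that case the high counts that prompted the removal are among those removed, and the month is rebuilt from calmer weeks.

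The SAP's argument for conservatism considers only the treated, quieter days that are dropped. It does not consider the attacks lost before treatment. At stake are the monthly counts in the Months 1-12 estimand and the monthly responder classifications. Eight of the 12 months (32/4) consist entirely of weekly entries.

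**Working it through.** **1. What each rule removes.** Take single-day use on day d of a diary week. Days 1 to 7 after use are the last 7 - d days of that week and the first d days of the next.

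| Use day d | Weekly rule | Daily rule with the 4-day minimum |
|---|---|---|
| 1-3 | both weeks removed | use week missing (d days left); next week kept (7 - d days) |
| 4-6 | both weeks removed | use week kept (d days); next week missing |
| 7 | next week only | next week only |

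For d = 1 to 6 the weekly rule deletes 14 days to exclude 7. The 7 valid days lost are the d days up to and including use and the 7 - d days after the exclusion window. If nothing else is missing, at least 2 weeks of the month remain, so it is prorated rather than set missing. Longer courses remove more: 2 to 3 entries for 3 to 7 days and 3 to 4 entries for 10 to 14 days. The month can then become missing.

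**2. First illustration (all counts assumed).** Baseline 40 per month; 5 attacks a week on days 1-14; 2 a day on days 15-18; treatment on day 18 (d = 4); none on days 19-28.
- Weekly rule: 4 x (5 + 5)/2 = 20, a 50% reduction (1 - 20/40).
- Daily rule: week 3 = 7 x 8/4 = 14 and week 4 is missing; 4 x (5 + 5 + 14)/3 = 32, a 20% reduction.
- Flare continuing untreated: 10 + 8 + 10 x 2 = 38, a 5% reduction.
- All recorded data: 10 + 8 + 0 = 18, a 55% reduction.
- Prorated over retained days: 28 x 18/21 = 24, a 40% reduction.

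**3. Second illustration (counts assumed).** Weeks 5-8 = 4, 14, 3, 4 attacks; use on day 5 of Week 6; baseline 32.
- Weekly rule: 4 x (4 + 4)/2 = 16, a 50% reduction.
- All recorded data: 4 + 14 + 3 + 4 = 25, a 22% reduction.

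If transitional treatment lowers counts, as the SAP expects, 25 is a lower bound for the target. Here the patient becomes a 30% and 50% responder through the deletion.

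**4. Range over use on days 1-28 (assumed).** Quiet rate 28 per month, flare of 1.5 to 3 times for 3 or 7 days, rate cut to 25% for 7 or 14 days after use.
- Weekly rule 26 to 59 against 32 to 68 untreated; lower in every flare scenario.
- Against the daily rule: 1.0 to 5.4 attacks lower if the effect lasts 7 days; from 3.9 lower to 1.4 higher if it lasts 14.
- Against all data: higher on average in every scenario.
- No flare, 7-day effect: weekly rule, daily rule and target all 28.0.
- No flare, 14-day effect: weekly rule 25.2, daily rule 23.8, target 28.0.

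**5. Simulation of affected months.** Assumed: 5 to 10 attacks a week; autocorrelated log daily rate (SD 0.6, lag-1 correlation 0.7-0.8); single-day use after a 3-day count at least twice the usual; 35-70% reduction for 7 days. The result depends on how the triggering day is chosen.
- Weekly rule: 14% to 20% below target.
- Daily rule: 1% to 9% below.
- Weekly score below the all-data score in 43% to 65% of affected months.
- In the runs with the weekly rule 18-19% below, all data were about 14% below and prorating over retained days was 3-5% below.
- Use unrelated to recent attacks: essentially no bias.

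**6. Trial level.** One run gave 30.6 against a target of 35.4, a gap of 4.8. If a share p of weekly-diary months is affected, the Months 1-12 mean shifts by 4.8 x 8/12 x p. For an assumed p of 5% to 20% that is 0.16 to 0.64 attacks a month.

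**The case against.** A reader might infer that the rule systematically scores in eptinezumab's favour. The documents do not support that. The direction depends on attacks being more frequent before treatment than in the retained weeks, and the documents give no data on what prompts transitional use. Use on day 7 spares the pre-treatment week, and long courses may leave the month missing. Against all recorded data, the rule gave higher counts on average throughout step 4, which is the comparison behind the SAP's wording; in step 5 the comparison went either way. These limits stand.

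Nor is the daily rule a clean benchmark. With its 4-day minimum it also discards the pre-treatment days for use on days 1-3, so its small average error partly reflects errors that offset each other. This stands too, and it shapes the fix.

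An all-data analysis of the long-term endpoint is already planned. It restores the pre-treatment attacks, but it also restores the treated days, so it does not isolate this effect. It does not reach the response endpoints.

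Finally, weekly entries may not be divisible. Panel 5 of the SAP scores them as a single pain value times a count, and the protocol has the patient record data for the week. Against this, Protocol 9.2.1.2, in a paragraph covering both daily and weekly recording, says "For each experienced cluster headache attack, the start date and time will be collected". The documents leave this open.

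**Conclusion.** The point holds conditionally. The weekly rule removes more than the hypothetical strategy requires. When transitional use follows a worsening, the DPS3 monthly count falls below the no-transitional target, by roughly 14% to 20% in affected months under the simulation assumptions above. The approach therefore cannot be called conservative without qualification for the long-term estimand or the monthly response endpoints. If use is unrelated to recent attacks, the deletion adds no bias; any shortfall then comes from an effect lasting beyond 7 days, which is a separate matter.

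The trial-level size cannot be computed because the frequency of use is not given. The short-term estimand uses daily-diary weeks and is not affected. Efficacy is a secondary objective without formal testing, so what is at stake is the accuracy of descriptive estimates and responder rates, not a test decision.

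**What to change.** In SAP 23.2.1.5, for weekly entries, use the attack start dates to remove only days 1 to 7 after use. Prorate the affected month over its retained days: 28 x (attacks on retained days)/(retained days). Keeping the 4-day weekly minimum would still discard pre-treatment days for use on days 1-3. This reduces the shortfall but does not abolish it: in the first illustration it gives 24 against 38, because the assumed effect outlasts 7 days.

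First confirm that weekly entries hold attack dates. If they do not:
- keep the current rule;
- extend the all-data (DPS1) analysis of 13.5.9.1 to the response endpoints;
- report the number of affected participant-months;
- qualify the statement in 13.5.1.1 that the approach is conservative.

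Scoring a removed week as the larger of its reported count and the mean of the month's other weeks should not be the primary derivation. It overstates attacks by about 5% to 6% when use is unrelated to a worsening.

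The cost is SAP wording and a little more derivation and analysis work. No new data are needed if the dates are held.

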23.2.1.6 Calculation of Assessments for Sensitivity Analyses

When doing the sensitivity analyses of the use of transitional treatment and withdrawal from treatment data will contain all data when considering the prorating.

23.2.1.7 Response

For the periods of time a participant will be eligible to count as a responder if at least 50% of the weeks are observed and:

- For 3-months intervals: at least 2 out of 3 months are observed
- For 6-months intervals: at least 4 out of 6 months are observed
- For 12-months intervals: at least 8 out of 12 months are observed

For participants fulfilling these criteria the average reduction of number of monthly attacks will be calculated and compared to the response threshold to evaluate if the participant is a responder. When finding the percentage of responders, the denominator will be the number of participants who fulfil these criteria.

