13.5.3 Long-term Efficacy Estimand

The long-term efficacy estimand is the mean change from Baseline in the monthly number of attacks (Months 1-12) for participants with chronic cluster headache receiving IV infusion of eptinezumab 400 mg every 12 weeks, without the use of transitional treatment (GON block and oral steroids), and with continuation of treatment eptinezumab 400 mg for 12 months, and regardless of use of abortive and preventive medication for cluster headache, and infusion interruption or termination before full dose is received.

The approach described in section 13.5.1 also apply for the long-term estimand with a few adjustments:

- The **clinical question of interest** is changes in cluster headache attacks within the 12 months after infusion with eptinezumab 400 mg.
- The **endpoint to be obtained to address the clinical question** is change from Baseline in the monthly number of attacks (Months 1-12)
- The **population level summary** will be the mean change across Months 1-12
- The **intercurrent events** use of transitional treatment and interruption or termination of IMP such that full dose is not received will be handled as in section 13.5.1. Furthermore, when the primary reason is either “Lack of Efficacy” or “Adverse Events” for withdrawal from treatment this will be considered an intercurrent event that will be handled by a hypothetical strategy

Intercurrent Events

In addition to the intercurrent events described above, the following intercurrent event, occurring after treatment initiation and potentially affecting either the interpretation or the existence of the measurements associated with the clinical question of interest, is considered.

- Withdrawal from treatment due to “Lack of Efficacy” or “Adverse events” –
Hypothetical strategy

For participants withdrawing from treatment, the majority of the effect is expected to be seen within the first 12 weeks following their last infusion and therefore data that occur beyond 12 weeks after their last infusion will not be considered.

Estimator

The intercurrent event withdrawal from treatment will be handled by a hypothetical strategy estimating the effect where all participants continue their treatment with eptinezumab 400 mg for 12 months by not including data collected 3 months or more after the latest infusion.

Furthermore, the following adjustments are needed compared to the estimator in section 13.5.1

- The week variable in the MMRM will be replaced by Month 1 to 12

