13.5.6.2 Efficacy Endpoints Regarding Response

For endpoints regarding response (30%, 50%, 75% or 100%) or sustained response (75%), the number and percentage of responders using weekly number of attacks for Week 1, Week 2, Week 3, Week 4, Week 5,, Week 48 and the number and percentage of responders using monthly number of attacks for Month 1, Month 2,, Month 12 will be presented without imputations other than described in section [13.5.1.1.1](#). Additionally, sensitivity analyses will be made using LOCF and worst case imputations, for further details see section [13.5.9.3](#). For all of these analyses DPS3 will be used when determining whether a participant is a responder or not.

Furthermore, the number and percentage of responders will be found for the following periods of time (for details see section [23.2.1.7](#)):

- Months 1-3, Months 4-6, Months 7-9, Months 10-12
- Months 1-6, Months 7-12

- Months 1-12

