13.5.9.3 Sensitivity Analyses to assess the impact of missing data regarding response

To assess the impact of only imputing data by prorating for response endpoints as described in section 13.5.6.2, LOCF and worst case imputations will be carried out for the endpoints regarding 75% response.

14 Safety

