23.2.1.4 Assigning Week to eDiary Assessments

The day of an infusion starts a new week e.g. the day of the first infusion is the first day of Week 1.

Weekly assessments coming from the eDiary will be assigned to a week using the day of an infusion as a starting point. Thus, the windowing showed in [Panel 6](#) will be applied.

Panel 6 Windowing of Weeks – Weekly eDiary Assessments

Days since IMP	First IMP	Second IMP	Third IMP	Fourth IMP
28 to 37	Week 5	Week 17	Week 29	Week 41
38 to 44	Week 6	Week 18	Week 30	Week 42

Days since IMP	First IMP	Second IMP	Third IMP	Fourth IMP
45 to 51	Week 7	Week 19	Week 31	Week 43
52 to 58	Week 8	Week 20	Week 32	Week 44
59 to 65	Week 9	Week 21	Week 33	Week 45
66 to 72	Week 10	Week 22	Week 34	Week 46
73 to 79	Week 11	Week 23	Week 35	Week 47
80 until the next IMP	Week 12	Week 24	Week 36	Week 48

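### Period response rates leave out participants with too little data, the planned missing-data check is limited to 75% response, and the data cut-off after treatment withdrawal has two conflicting start dates

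*SAP*

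**What the plan says.** **Who counts.** SAP 13.5.6.2 plans responder percentages for Months 1-3, 4-6, 7-9, 10-12, 1-6, 7-12 and 1-12. Under 23.2.1.7 a participant needs at least half of the weeks, plus 2 of 3, 4 of 6 or 8 of 12 months; for the longest period, "For 12-months intervals: at least 8 out of 12 months are observed". On the percentage itself: "When finding the percentage of responders, the denominator will be the number of participants who fulfil these criteria". Participants who fall short leave both numerator and denominator.

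**Which data.** Section 13.5.6.2 states: "For all of these analyses DPS3 will be used when determining whether a participant is a responder or not". DPS3 removes data after treatment withdrawal. Section 13.5.3 applies this when the primary reason is lack of efficacy or adverse events, and counts from the last infusion: "therefore data that occur beyond 12 weeks after their last infusion will not be considered".

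**The cut-off rule.** The first sentence on treatment withdrawal in 23.2.1.5 agrees with that: "data that are collected 3 months or more after the latest infusion will be excluded". The next sentence, for daily entries, has a different start date: "data occurring 84 days or more after the date for withdrawal from treatment will be removed".

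**The sensitivity check.** Section 13.5.9.3 says: "LOCF and worst case imputations will be carried out for the endpoints regarding 75% response". Chapter 22 lists 75% response among the endpoints added by the SAP. The protocol (section 2, Panel 3) has 30%, 50% and 100% response in monthly attacks as exploratory endpoints, for the periods between infusions and the 12 weeks after the last. The 6- and 12-month response periods appear only in the SAP.

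**The concern.** The period rates are observed-case percentages, and part of the exclusion is tied to outcome: someone who stops for lack of efficacy loses later diary data by rule, even if the diary is kept up. In a single-arm trial these percentages will be read at face value. If those left out respond less often than those who stay, the rates are too high, and later periods can look better than earlier ones with no change in effect.

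The one planned check on missing response data is tied to a threshold the protocol does not contain. The all-data rerun after treatment withdrawal (13.5.9.2) is limited to the monthly-attack model of 13.5.3, so it does not reach response either.

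The two start dates in 23.2.1.5 are a separate matter and reach further. Counting from the withdrawal date can keep data that the long-term estimand sets aside, in every DPS3 analysis.

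**Working it through.** **Inputs.** Planned 125 treated, 100 completers, 20% withdrawal (protocol 16.11, SAP chapter 20). A month counts as observed with at least 2 of 4 weeks (SAP 23.2.1.3). Eligibility is from 23.2.1.7. Assumed, because the documents give no figure: FAS = 125, withdrawal spread evenly over 48 weeks, complete diary until leaving, observed response 50%.

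**Plan's own figure.** 100 / (1 − 0.20) = 125, which reproduces.

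**Step 1: last diary week needed.** For Months 4-6, month 4 must be observed and month 5 needs two weeks, so the diary must reach Week 18; that is 6 of 12 weeks and meets the 50% rule. In the same way, Months 1-3 need Week 6, Months 7-9 Week 30, Months 10-12 Week 42, Months 1-6 Week 14, Months 7-12 Week 38 and Months 1-12 Week 30.

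**Step 2: share excluded and worst case.** Share excluded e = 0.20 × week / 48. The rate over the whole FAS is 50 × (1 − e) if all excluded are non-responders.

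| Period | Week needed | e | Participants | Worst case |
|---|---|---|---|---|
| Months 1-3 | 6 | 2.5% | about 3 | 48.75% |
| Months 4-6 | 18 | 7.5% | about 9 | 46.25% |
| Months 7-9 | 30 | 12.5% | about 16 | 43.75% |
| Months 10-12 | 42 | 17.5% | about 22 | 41.25% |
| Months 1-12 | 30 | 12.5% | about 16 | 43.75% |

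If the excluded respond as often as the others, every rate stays at 50%. At Months 10-12 the ratio of observed to worst-case rate is 1 / (1 − 0.175) = 1.21.

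**Step 3: what DPS3 does to treatment stoppers.** Counted from the latest infusion, stopping after 1, 2 or 3 infusions keeps Weeks 1-12, 1-24 or 1-36.
- After 1 infusion: eligible only for Months 1-3.
- After 2: out of Months 7-9, 10-12, 7-12 and 1-12.
- After 3: out of Months 10-12 and 7-12.

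All such stoppers are therefore out of Months 10-12. Suppose s of the planned 20% are stoppers who keep the diary, and the rest leave the study evenly. Since 42/48 = 0.875, e at Months 10-12 is (0.20 − s) × 0.875 + s.
- s = 5%: 0.15 × 0.875 + 0.05 = 18.1%; worst case 40.9%; factor 1.22.
- s = 10%: 0.10 × 0.875 + 0.10 = 18.75%; worst case 40.6%; factor 1.23.

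**Step 4: the two start dates.** Take a withdrawal recorded on day 83 after a single infusion. From the infusion, data from day 84 on are removed. From the withdrawal date, removal starts at day 83 + 84 = 167. What this does to period eligibility cannot be worked out. Section 23.2.1.4 says "Weekly assessments coming from the eDiary will be assigned to a week using the day of an infusion as a starting point", and the last row of Panel 6 runs until the next infusion, so weeks after a skipped infusion have no defined number.

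**The case against.** **The threshold limit matters little for worst case.** Eligibility does not depend on the threshold, so the worst-case rate is the observed rate times (1 − e) at 30%, 50%, 75% or 100% alike. One 75% table covering the periods would show e for all of them, and a reader could derive the rest from the planned responder counts and the FAS size. This is right as arithmetic. What stands is that 13.5.9.3 does not say whether it covers the periods, and no worst-case rate is planned beside the protocol's own thresholds.

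**Other displays exist.** Section 13.5.6.1 plans model estimates of monthly attacks for the same periods, and 13.5.7 states that the model uses participants who withdraw or have missing data. Attrition is shown in 8.2, chapter 12 and 13.5.5. A reader might infer that long-term efficacy rests on the response rates alone; it does not.

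**No breach of the protocol.** Protocol 16.8.2 leaves diary derivation and imputation to the SAP, so a reader who sees a protocol departure here would be wrong.

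**Larger figures are not supported.** A reader might add 10% treatment stoppers on top of the 20%, giving 17.5 + 10 = 27.5% excluded at Months 10-12 and a factor of 1 / 0.725 = 1.38. The documents give no such extra loss. The trial aims at 100 participants with 1-year exposure, which under 23.2.2 requires four infusions; 125 × 0.70 = 87.5 would miss that aim.

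**Worst case changes the question.** Scoring participants whose later diary data DPS3 removed as non-responders alters how treatment withdrawal is handled, as well as how missing data are handled. This is correct, and the added analysis must be labelled so.

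**Conclusion.** The concern holds as a low-cost improvement in reporting, together with one rule that is wrong as written.

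The period response rates describe participants with sufficient data, not the FAS. Within the planned 20% withdrawal, an observed 50% at Months 10-12 corresponds to between 50% (excluded respond alike) and 41.25%, or 40.9-40.6% if 5 to 10 points of the 20% are treatment stoppers. The gap is about 1 point at Months 1-3. These figures rest on even withdrawal, complete diaries and an assumed 50% rate. Diary gaps and removals after transitional treatment would add exclusions that the documents do not let one quantify.

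The direction of any bias is not established: the documents give no response rate for withdrawers, and if they respond more often the rates are too low. With no testing, neither type I error nor power is at issue.

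The 84-day sentence in 23.2.1.5 contradicts its own first sentence and 13.5.3. Its effect on the results cannot be sized.

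**What to change.** 1. Keep 23.2.1.7 as the main summary, label it 'response among participants with sufficient data', and show the number excluded for each period.
2. Extend the worst-case analysis in 13.5.9.3 to 30%, 50%, 75% and 100% and to all 3-, 6- and 12-month periods. Anyone short of the criteria counts as a non-responder, the denominator is the full FAS, and the result stands next to the observed-case rate. State that it counts both missing data and treatment withdrawal as non-response, and so is a bound under a different intercurrent-event strategy from that of 13.5.3.
3. Change the 84-day sentence in 23.2.1.5 to count from the latest infusion, and state how weeks are numbered after a skipped infusion.

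The cost is SAP wording and re-use of the programs planned for 75% response. The downside is a few more tables and less favourable rates beside the main ones. The main analysis and the hypothetical strategy are unchanged.
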